APPENDIX 1. COVID-19 PANDEMIC RELATED PROTOCOL ADAPTATIONS

The table below summarizes adaptations made to the FAM-ACT study protocol to accommodate restrictions on research recruitment and conduct during the COVID-19 pandemic. For additional detail on these adaptations see our 2022 publication in *Trials*:

Deverts DJ, [name], [name], [name], [name], [name], Guajardo C, Ilaraza-Montalvo D, [name], Koerbel G, [name]. Comparing the effectiveness of Family Support for Health Action (FAM-ACT) with traditional community health worker-led interventions to improve adult diabetes management and outcomes: study protocol for a randomized controlled trial. Trials. 2022 Dec;23(1):1-22.

ORIGINAL PROTOCOL	ADAPTED PROTOCOL
ELIGIBILITY CRITERIA	
The study planned to examine 5-year diabetes-specific cardiac risk (UK Prospective Diabetes Study [UKPDS] score) as a secondary outcome. Thus, adults with diabetes were eligible to participate if (a) their most recent HbA1c is $\geq 8.0\%$ and/or (b) have poor blood pressure control (SBP >150 mm Hg), recorded in the FQHC EMR at least twice in the past 6 months, with the most recent SBP being >150 mm Hg.	Because UKPDS score was dropped as an outcome (see Outcomes/Secondary outcomes), poor blood pressure control no longer is being used as an inclusion criterion, thus requiring all patient participants to qualify based on their HbA1c. Eliminating the blood pressure criterion effectively reduces the size of our eligible patient pool. To compensate for this limitation, the HbA1c criterion has been lowered to $\geq 7.5\%$.
LENGTH OF INTERVENTION PROTOCOL	
Both the FAM-ACT and I-DSMES interventions were designed to last 12 months, with the introductory and DSMES sessions completed during the first 6 months of the protocol, and CHW care management contacts continuing throughout the subsequent 6 months. Most study contacts occurred in the first 6 months of the 12-month period.	The intervention has been condensed to 6 months to compensate for (a) the several-month pandemic-related pause in research recruitment and (b) the additional time needed to make substantial changes to the study and intervention. The shorter protocol permits full sample recruitment, with time to complete the protocol, within the timeframe of study funding.
INTRODUCTORY AND DSME SESSION DELIVERY	
Intervention sessions were designed to be delivered in-person at the FQHC, with each session lasting 1.5 to 2 hours. Conducting the group sessions in-person enables the CHW to use the ADA-approved DSMES Conversation Maps® and other visual aids. This hands-on approach is designed to encourage participant engagement with the material and give participants an opportunity to interact with other patients with diabetes. The face-to-face setting also facilitates communication and relationship-building between participants and the CHW.	To accommodate restrictions on in-person and group contact during the height of the pandemic, introductory sessions and DSMES sessions for both interventions have been redesigned for virtual platform delivery (Zoom). Several changes were made to both the structure and content of the sessions, including reducing the duration of the sessions to 45-60 minutes, replacing the DSMES Conversation Maps® with online PowerPoint slides and creating revised facilitator guides that are better suited to virtual delivery of the DSMES intervention.
BIWEEKLY CARE MANAGEMENT CONTACTS	
CHW contacts were designed to be delivered predominantly by phone or video chat, but also in-person at the FQHC during clinical visits, or at the participant's home if necessary.	To accommodate social distancing guidelines and participant and CHW health precautions, in-person care management contacts have been eliminated.

ORIGINAL PROTOCOL	ADAPTED PROTOCOL
PARTICIPANT MATERIALS	
Per the original procedure, the CHW was responsible for distributing workbooks and printed handouts. Workbooks were to be given to participants when they met with the CHW for the introductory session, and topical handouts were to be distributed during the relevant DSMES session.	To accommodate those who attend sessions virtually, patients now receive all educational materials at their baseline assessment. FAM-ACT only: If the patient and SP live together, the patient also is given the SP's materials. If they live separately, the RA will mail the SP their materials.
OUTCOMES	
Primary outcome: The original primary outcome was change in patient HbA1c from baseline to 12 months post-baseline, reflecting the original intervention length of 12 months.	Primary outcome: The primary outcome was revised to change in HbA1c from baseline to 6 months, reflecting the adapted intervention length of 6 months.
Secondary outcomes: The original analysis plan included 6-month and 12-month change in patient UKPDS score as a secondary outcome. The calculation of UKPDS score is based on HbA1c, SBP, cholesterol levels, and smoking status.	Secondary outcomes: Change in UKPDS score has been dropped as a secondary outcome because patient cholesterol cannot be measured reliably without in-person assessment. A substantial number of first wave patients became eligible for their 6-month assessment while restrictions on in-person research activities were in effect.
SAMPLE SIZE	
See analysis plan	
DATA COLLECTION	
HbA1c: Per the original protocol, patients were to have their HbA1c assessed at 3 time points: baseline, 5 to 7 months post-baseline and 11 to 13 months post-baseline. All assessments were to be conducted by study RAs using the fingerstick method described above.	HbA1c: To accommodate pandemic-related restrictions on in-person research activities, 2 additional HbA1c assessment methods have been incorporated into the protocol. Clinic measures. Tests unable to be obtained in-person during the assessment window will be recorded from patients' EMRs rather than obtained via a study staff-conducted assessment. Home testing. Patients may be offered the option to self-test their HbA1c using a fingerstick device (e.g. A1cNow® Self Check, pts Diagnostics) sent to their home.
Survey assessments: As part of the original protocol, SPs were to be assessed by survey at 2 timepoints: baseline and 11-13 months post-baseline.	Survey assessments: Because the duration of the study protocol was decreased from 12 to 6 months, SPs now will be surveyed at baseline and 6-9 months post-baseline.

CHW, community health worker; DSMES, diabetes self-management education and support; EMR, electronic medical record; FAM-ACT, Family Support for Health Action; FQHC, Federally Qualified Health Center; HbA1c, hemoglobin A1c; I-DSMES, individual patient-focused diabetes self-management education and support; SBP, systolic blood pressure; SP, support person; UKPDS, UK Prospective Diabetes Study

APPENDIX 2. FAM-ACT STUDY GUIDE TO SUICIDAL PARTICIPANTS

[figure not shown]
Suicidal Ideation: If a FAM-ACT participant volunteers information about suicidal ideation, like:

- I'd rather not be alive anymore
- I want to sleep and never wake up
- I can't take it anymore
- I don't know what I might do

The FQHC research study team member will complete the *Participant Suicide Risk Screening Questions* on the next page, and follow the instructions for the correct action step.

Participant Suicide Risk Screening Questions:

Instructions: Circle all responses, and then follow instructions for Action Steps according to "CONNECT Staff Action Steps for PSRS"

Action Step 1:**In-Person or on the telephone:**

If the respondent reports NO active suicidal thoughts, plans, or intent, reply to the patients with the following bullets, and continue the study:

- Thank you for your responses. I am glad that you are not thinking of harming yourself. Any thoughts that you would be better off dead are worrisome and I strongly suggest that you talk with your regular mental health professional or doctor about this soon.
- I would like to give you this list of Mental Health providers in case you may have these thoughts again.
- I would also like to give you the toll-free **National Suicide Prevention Lifeline: [name]**. The National Suicide Prevention Lifeline is a national network of local crisis centers that provides free and confidential emotional support to people in suicidal crisis or emotional distress 24 hours a day, 7 days a week. We're committed to improving crisis services and advancing suicide prevention by empowering individuals, advancing professional best practices, and building awareness

Action Step 2:**In-Person or on the telephone:**

If the respondent reports ANY active suicidal thoughts or plan but indicates that he/she has NO intent to act on those thoughts within the next few days, provide him/her with the same information provided in **Action Step 1**.

Action Step 3:**On-Site at FQHC:**

If the respondent reports that it is either "somewhat likely" or "likely" that he or she will "harm himself (or herself) or end his (or her) life over the next few days," or engaged in suicidal or high-risk behavior, provide him/her with the following information:

- I am very concerned about your thoughts of harming yourself (or high-risk behavior) and I think it is very important that you speak with a mental health professional about these thoughts right away. What I would like for you to do now is talk with the FQHC mental health specialist currently here.

On the Telephone with the Participant or Off-Site:

If the respondent reports that it is either "somewhat likely" or "likely" that he or she will "harm himself (or herself) or end his (or her) life over the next few days," or engaged in suicidal or high-risk behavior, provide him/her with the following information:

Call the National Suicide Prevention Lifeline number together with the participant immediately: Lifeline: [name]

The National Suicide Prevention Lifeline is a national network of local crisis centers that provides free and confidential emotional support to people in suicidal crisis or emotional distress 24 hours a day, 7 days a week. We're committed to improving crisis services and advancing suicide prevention by empowering individuals, advancing professional best practices, and building awareness.

*If the participant is severely distressed and the FQHC Research Study Team Member feels the participant may hurt themselves imminently, they should call 911.

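### Suicide-risk guide: Action Step 2 reuses an Action Step 1 sentence that is false for respondents with active suicidal thoughts or a plan

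*Protocol*

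**What the plan says.** Protocol Appendix 2 sets out what a study team member does when a participant volunteers suicidal ideation. The team member asks the screening questions and then follows one of three action steps.

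- **Action Step 1** is for respondents who report no active suicidal thoughts, plans or intent. Staff are told to "reply to the patients with the following bullets, and continue the study". The first of three bullets thanks the respondent and then says "I am glad that you are not thinking of harming yourself". It goes on with "Any thoughts that you would be better off dead are worrisome" and advice to see a professional soon. The second bullet offers a list of mental health providers, and the third gives the Lifeline.
- **Action Step 2** has this trigger: "If the respondent reports ANY active suicidal thoughts or plan but indicates that he/she has NO intent to act on those thoughts", the time frame being the next few days. The instruction is to "provide him/her with the same information provided in" Action Step 1. Nothing is excepted or added.
- **Action Step 3** is for respondents who say it is somewhat likely or likely that they will harm themselves within days, or who have engaged in suicidal or high-risk behavior. On site, staff are told to "provide him/her with the following information", and a spoken script follows that begins "I am very concerned about your thoughts of harming yourself". By telephone or off site, the same lead-in is followed by a staff action: "Call the National Suicide Prevention Lifeline number together with the participant immediately".

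**The concern.** Step 1 and Step 2 separate respondents by whether they report active suicidal thoughts or a plan. A reply written for people without such thoughts cannot be passed whole to people who have them, because it contains a sentence stating that they have none.

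What is at stake is what an at-risk participant hears. Someone who has just disclosed active thoughts or a plan would be told that staff are glad this is not so. That contradicts the disclosure just when the guide needs the person to accept the provider list and the Lifeline. Under the Protocol section on procedures conducted in both arms, community health workers, their manager and research assistants conduct all participant contacts, so the people using the guide may lean on its wording.

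**Working it through.** No arithmetic beyond a count applies. The check sets the entry conditions against the reused text and then looks for any other text that would correct it.

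**1. Entry conditions against the reused sentence**

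| | Action Step 1 | Action Step 2 |
|---|---|---|
| Active suicidal thoughts or plan | None reported | Reported |
| Intent to act | None reported | None within the next few days |
| Reply | Three scripted bullets | The same as Step 1, no exception |
| Is "I am glad that you are not thinking of harming yourself" true? | Consistent with what was reported | False |

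The contradiction follows from the text itself. It needs no assumption about how often Step 2 is used.

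**2. How much of Step 1 is affected**

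Scripted sentences in Step 1: bullet 1 has 3, bullet 2 has 1, bullet 3 has 3, so 3 + 1 + 3 = 7. One is false for a Step 2 respondent, the 11-word second sentence of bullet 1. That leaves 7 − 1 = 6:

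- The opening thanks, the line calling such thoughts worrisome with its advice to see a professional, and the three Lifeline sentences all still apply.
- The provider-list sentence offers the list in case the thoughts return. That sits awkwardly with thoughts that are current, but it is not false.

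**3. Does Step 2 call for the script, or only for its contents?**

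The Step 1 reply consists only of scripted bullets, so the cross-reference has nothing else to point to. On-site Step 3 uses "provide him/her with the following information" to introduce first-person speech, which supports reading Step 2 as a script. Telephone Step 3 uses the same words before a staff action, so usage is mixed. The script reading is the natural one but not the only one.

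**4. Does other Protocol text remove the sentence?**

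- The note at the end of Appendix 2 directs a 911 call when staff think the participant may hurt themselves imminently.
- The sections on privacy and confidentiality and on participant privacy let the PI or Site-PI decide to contact a patient's physician when the patient appears to be in danger.
- The steps for a clinically significant unexpected condition provide for notifying the study leads, for referring patients to their provider or to emergency services, for offering to contact that provider, and for advising support persons to contact their own.
- The section on serious adverse events requires immediate reporting of adverse events and potential problems.

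Each adds something around the conversation. None changes what Step 2 tells staff to say.

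**5. Is the guide operative?**

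Yes. Appendix 2 itself directs staff to complete the screening questions and follow the matching step. The risk section also says the team will follow an attached suicide protocol when a support person shows signs of suicide. Appendix 2 is the only such guide visible, although its title differs, so that they are the same document is an inference.

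**The case against.** The strongest reply is that Step 2 does not ask for a verbatim repeat. Step 1 tells staff to reply with the bullets; Step 2 tells them to provide information. An expression of relief is not information, whereas the provider list and the Lifeline are, and Step 1 introduces both as things to be given. On that reading the false sentence is never spoken. This stands as a possible reading, and telephone Step 3 lends it some support. It does not settle the matter, because Step 2 excludes nothing and on-site Step 3 uses nearly the same phrase for speech. A crisis guide should not depend on staff choosing the lenient reading. If some already do, the correction makes that practice uniform.

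Second, the appendix refers staff to CONNECT action steps that are not visible, and the screening items are missing from the available text. Those action steps might give separate Step 2 wording. This also stands, and it is why the corrected wording should be checked against them.

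Third, the consequence is small. The respondent still gets the advice, the list and the Lifeline, and the other safeguards remain. That is accepted. It limits the weight of the point but not its correctness.

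Fourth, there is a broader question: Step 2 names no clinician contact of its own, so its reply to active thoughts or a plan is the same as the reply to none. That is a separate clinical matter. This point neither resolves it nor clears the rest of Step 2.

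**Conclusion.** The concern holds as a wording error in an operative safety script. One of the seven sentences that Step 2 takes over is false for everyone who meets its trigger, and no other visible text removes it. The conclusion rests on two assumptions: that staff read Step 2 as calling for the Step 1 script, which is the natural but not the only reading, and that the unseen CONNECT steps do not already supply different wording.

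Its reach is limited to participants who volunteer suicidal ideation and then meet the Step 2 trigger, a number the documents do not give. It has no bearing on endpoints, sample size or analysis. It is minor in consequence but should be corrected, because the listener is a person at risk and the correction is very cheap.

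**What to change.** Keep the cross-reference in Action Step 2 and add one exception: staff give the Step 1 content except the sentence "I am glad that you are not thinking of harming yourself", and in its place say *Thank you for telling me about these thoughts.* The rest of the Step 1 content carries over as it is, and triggers and referral rules do not change.

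The responsible clinicians should approve the replacement and check it against the CONNECT action steps. They may prefer other words, since the Step 1 script already opens with thanks; what matters is that the false sentence goes. While they have the text open, they can also decide whether the provider-list sentence should refer to present thoughts.

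The cost is one added clause in Appendix 2, clinician approval and a note to trained staff.

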1.0 INTRODUCTION

This statistical analysis plan (SAP) describes the statistical methods to be used for analyzing and reporting data collected for the Family Support for Health Action (FAM-ACT), a randomized, parallel-arm, comparative effectiveness trial.

2.0 STUDY OBJECTIVES

FAM-ACT aims to compare the effectiveness of a family supporter-focused (FAM-ACT) intervention relative to an individual patient-focused diabetes self-management education and support (I-DSMES). Specifically:

1. Determine the effectiveness of FAM-ACT, compared to I-DSMES, in improving patients' diabetes-related health outcomes (primary: Hemoglobin A1c [HbA1c]; secondary: blood pressure)
2. Determine the effectiveness of FAM-ACT, compared to I-DSMES, in improving patients' health behaviors and perceived support
3. Examine theoretical-model-driven moderators and mediators of FAM-ACT participation on patient outcomes

3.0 STUDY DESIGN

This is a randomized, parallel-arm, comparative effectiveness trial designed to test effectiveness of FAM-ACT in improving diabetes health outcomes and self-management behaviors and perceptions among patients with type 2 diabetes. The study arms consist of:

- Treatment arm: FAM-ACT
 - Patient and Support Person/SP (dyad) will receive a Diabetes Complications Risk Assessment profile and introduction session, SP-focused information/skills training through 4-6 extended DSME sessions, case management contacts with a Community Health Worker (CHW) throughout

the duration of the 6-month intervention, and guidance on how to prepare for and participate in healthcare appointments.

- Control arm: I-DSMES
 - Patient only will receive a Diabetes Complications Risk Assessment profile and introduction session, 4-6 group DSME sessions, case management contacts with CHW throughout the duration of the 6-month intervention, and guidance on how to prepare for and participate in healthcare appointments.

3.1 SAMPLE SIZE AND POWER CONSIDERATIONS

We powered our study to detect a clinically meaningful difference in our primary outcome HbA1c at 6 months (Aim 1) based on a linear mixed model with intervention arm, linear time (0, 6, and 12 months), and interaction between intervention arm and time. We assumed that, due to randomization, the mean difference at baseline is zero and that the intervention effect is represented by the between group difference in time slope (captured by the intervention arm by time interaction), or equivalently, differences at follow-up time points. All calculations assumed at least 80% power and two-sided tests at level $\alpha = 0.05$ using the R package `longpower` (1). The standard deviation of HbA1c at any given time point was estimated to be between 1.5% to 2.2% based on previous studies (2–5). The correlation between timepoints, as measured by the intra-class correlation coefficient (ICC) ranged from 0.5 to 0.7 based on the RCT data at the Federally Qualified Health Center (FQHC) where the study is being conducted. Table 1 shows the total sample size required for various intervention effects.

Table 1: Total sample size (N) required for different intervention effects assuming a range of ICCs and SDs for *HbA1c*

SLOPE DIFFERENCE	MEAN DIFFERENCE AT 6 MONTHS	ICC	SD			
			1.50%	1.75%	2.00%	2.20%
0.067	0.40%	0.5	442	601	785	950
		0.6	354	481	628	760
		0.7	265	361	471	570
0.083	0.50%	0.5	283	385	503	608
		0.6	227	308	402	487
		0.7	170	231	302	365
0.010	0.60%	0.5	197	268	349	423
		0.6	157	214	280	338
		0.7	118	161	210	254
0.116	0.70%	0.5	145	197	257	311
		0.6	116	157	206	249
		0.7	87	118	154	187

To detect a 6-month mean difference of 0.6% in HbA1c, the total sample size required is 214 (highlighted in table above). We chose this sample size based detecting a clinically meaningful effect while considering the study size recruitment feasibility. The detectable effect is similar to what was observed in prior studies. We assumed an HbA1c standard deviation (SD=1.75%) and ICC (ICC=0.6) within the range of potential values reported in the

literature. If these estimates were conservative (i.e., if true SD=1.5% and true ICC=0.7), our sample size achieves at least 80% power to detect mean difference as small as 0.4%.

Anticipating 20% attrition based on the rate observed in prior 6-month and 12-month RCTs at the FQHC, we propose to recruit a total of 268 dyads (134 per group).

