4.0 STUDY ENDPOINTS AND COVARIATES

4.1 PRIMARY ENDPOINT

The primary outcome is the change in patient glycemic control from baseline to 6 months. Glycemic control is measured by HbA1c in %.

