5.2 ANALYSIS OF PRIMARY EFFICACY ENDPOINT (AIM 1)

The primary analysis will be intent-to-treat (ITT). Section 6.0 discuss details of how missing data and intercurrent events (ICEs) will be analyzed. We will test the hypothesis that the change in HbA1c from baseline to 6 months differed between FAM-ACT and individual focused arm.

We will first graphically examine how HbA1c change over time. We will then conduct our main analyses using linear mixed-effects models that include repeated measures at baseline, 6 months, and 12 months. To evaluate the effect of the intervention over time, we will include time in the model plus an interaction term for time x intervention arm. We will also explore models with time as a categorical instead of continuous variable and use the model that fits best, based on Akaike's Information and Schwarz's Bayesian Criteria. The primary hypotheses (change from baseline to 6 months) will be tested using appropriate linear contrasts. Treatment effect estimates will be presented along with 95% confidence intervals. The model will be adjusted for our design variables (baseline HbA1c and whether the patient and SP live together), baseline insulin use, and age. If baseline HbA1c and insulin use are highly correlated, we will prioritize HbA1c in the primary model and adjust for insulin use in sensitivity analyses.

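### SAP 3.1 claims at least 80% power for a 0.4% HbA1c difference, but its own Table 1 requires 265 patients for that case and the plan provides 214 (about 71% power)

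*SAP*

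**What the plan says.** SAP 3.1 describes a power calculation "based on a linear mixed model with intervention arm, linear time (0, 6, and 12 months") with an arm-by-time interaction, at 80% power and two-sided 5% significance. Table 1 gives total N for four differences at 6 months (0.40% to 0.70%), three ICCs and four SDs.

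The design cell has SD 1.75% and ICC 0.6: "To detect a 6-month mean difference of 0.6% in HbA1c, the total sample size required is 214". The next step is a favourable scenario. If the true SD is 1.5% and the true ICC is 0.7, "our sample size achieves at least 80% power to detect mean difference as small as 0.4"%. The paragraph after that reads "Anticipating 20% attrition based on the rate observed in prior 6-month and 12-month RCTs at the FQHC", and "we propose to recruit a total of 268 dyads (134 per group").

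The endpoint matches the table's column heading. Section 4.1 states: "The primary outcome is the change in patient glycemic control from baseline to 6 months".

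**The concern.** The favourable scenario is itself a cell of Table 1. At SD 1.50% and ICC 0.7 the table requires 265 for a 0.40% difference and 170 for 0.50%. The chosen 214 lies between the two. The table therefore supports 80% power for 0.50% but not for 0.40%, where 214 is 265 − 214 = 51 patients short.

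What is at stake is how the primary result is read. If the trial shows no difference, the sentence invites the argument that a 0.4% effect would probably have been detected. On the table's own basis the chance of missing such an effect is about 29%, not at most 20%, and that is under the most favourable SD and ICC the SAP considers.

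**Working it through.** **Inputs, from SAP 3.1 unless noted.** Two-sided alpha 0.05; power 80%; 1:1 allocation (Protocol, Overview of Study Design); design case d = 0.6, SD 1.75, ICC 0.6, N = 214; favourable case d = 0.4, SD 1.5, ICC 0.7, table N = 265; attrition 20%; 268 recruited. z(0.975) + z(0.80) = 1.960 + 0.842 = 2.802.

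**1. Reproduce the plan's own figures.** Take the change from baseline to 6 months, with variance 2·SD²·(1 − ICC):

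N = 4 × 2.802² × 2·SD²·(1 − ICC) / d², rounded up.

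- Design case: 213.7, so 214 as stated.
- Favourable case: 264.9, so 265 as stated.
- All 48 cells of Table 1 are matched.
- Attrition: 214 / 0.8 = 267.5, so 268 as stated; 268 × 0.8 = 214.4.

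**2. Power in the favourable case.** At N = 214, SE = √(4 × 2 × 1.5² × 0.3 / 214) = 0.1589. Power for 0.4% is Φ(0.4 / 0.1589 − 1.96) = 0.712 (0.708 with the t distribution). The difference detectable with 80% power is 2.802 × 0.1589 = 0.445%.

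| Patients with complete data | Power for 0.4% |
|---|---|
| 214 | 71.2% |
| 264 | 79.9% |
| 265 | 80.0% |
| 268 | 80.5% |

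For a 0.5% difference, power at 214 is about 88%.

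**3. Baseline-adjusted variant (an assumption).** For a two-visit analysis of covariance the residual variance is SD²·(1 − ICC²). SE = √(4 × 1.5² × (1 − 0.49) / 214) = 0.1465, which gives 78.0% power. The N needed for 0.4% is 225.2, so 226. To reach 80% at 214, the other covariates would have to remove a further 1 − 214/225.2 = 5.0% of residual variance. The SAP gives no such figure. This is not the basis of Table 1 either: it would give 171 for the design cell.

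**4. The model described in the text.** With linear time at 0, 6 and 12 months, the squared deviations of time sum to 72. Taking slope = d/6:

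N = 4 × 2.802² × SD²·(1 − ICC) / (72 × slope²).

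This gives 53.4 (54) for the design cell and 66.2 (67) for the favourable cell, and it matches none of the 48 cells. Table 1 does fit:

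- a 6-month contrast from visits at 0 and 6 months;
- a 6-month contrast from three visits with categorical time, under compound symmetry;
- a linear 0/6/12 model if the listed differences were 12-month differences, but the column heading, the text and section 4.1 all say 6 months.

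**5. Printed slopes.** In the 0.60% row, 0.60 / 6 = 0.100, but 0.010 is printed. The N values in that row correspond to 0.60%, so the misprint does not affect them.

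**The case against.** The strongest defence is that the sample size in the sentence means 268. The analysis is intent-to-treat with mixed models, and 268 exceeds 265, giving 80.5%. But the sentence follows the choice of 214 and precedes the attrition step. On this reading the claim also survives the loss of only 268 − 265 = 3 patients (1.1%), while the next paragraph plans for 20%. The reading may explain how the sentence arose; it does not make it right.

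A second defence is that 71% is the lowest of several figures. Section 5.2 adjusts for baseline HbA1c, and the linear 0/6/12 model with 6-month labels would give 99.9% at 214. The adjusted figure of 78.0% is closer, but it is still below 80%. The 99.9% cannot be used without abandoning Table 1 and the justification for 214. It also relies on 12-month visits, which the Protocol (footnote to Table 1) makes conditional on the study timeline. A one-sided 5% test would give 80.9%, but the SAP specifies two-sided tests.

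Third, 0.445 rounds to 0.4 at one decimal. That is possible, but 0.40% and 0.50% are separate rows with different N, and rounding the effect downward cannot support a claim of at least 80%.

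What stands is a limit on the consequence. The sentence set nothing in the design, and section 5.2 commits to 95% confidence intervals, which will show directly whether 0.4% is excluded. It also stands that the documents do not contain the longpower call, so which of the calculations fitting Table 1 was run cannot be known. Section 5.2 leaves the form of time open as well: "We will also explore models with time as a categorical instead of continuous variable".

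**Conclusion.** The power statement is wrong as written. On Table 1's unadjusted basis, with SD 1.5%, ICC 0.7 and 214 patients, power for 0.4% is about 71%, roughly 9 percentage points below the claim, and the 80%-power difference is about 0.445%. The contradiction with the 265 cell needs no outside assumption. The 71% rests on the recovered formula; the 78% rests on an assumed two-visit adjustment.

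The error is confined to this secondary statement, but it concerns the primary endpoint and is worth correcting. The mismatch between model wording and table, and the misprinted slope, are separate clarifications on which this conclusion does not depend.

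**What to change.** Restate the sentence along these lines: if SD = 1.5% and ICC = 0.7, 214 evaluable patients give 80% power for a difference of about 0.45% (about 71% for 0.4%). Keep 214, 268 and the 0.6% target.

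As clarifications, check the stored longpower inputs, make the described model agree with the calculation behind Table 1, and change the slope in the 0.60% row from 0.010 to 0.100.

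The cost is one sentence, one table entry and one check, with the model description reworded to match. One stated figure becomes slightly less favourable.
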